10.8.9. Statistical Considerations for Substudy B

See Section 9 for master protocol statistical considerations and substudy specifics below.

10.8.9.1. Statistical Hypotheses

10.8.9.1.1. Estimands

The estimands corresponding to the primary objectives are described in the table in Section 10.8.3.

In the primary safety objective evaluations, missing AE start dates will be imputed according to Pfizer safety rules. No other missing information will be imputed in the safety analysis.

10.8.9.1.2. Statistical Hypotheses

All objectives in this substudy are descriptive. No hypothesis testing is planned.

10.8.9.1.3. Multiplicity Adjustment

No multiplicity adjustment is needed for the study as there is no statistical hypothesis.

10.8.9.2. Analysis Sets

For the purpose of analysis, the following analysis sets are defined for this substudy:

| Population | Description |
|------------|---|
| Enrolled | All participants who have a signed ICD. |
| Randomized | All participants who are assigned a randomization number in the IWR system. |
| Safety | All participants who receive at least 1 dose of the study intervention. |

10.8.9.3. Statistical Analyses

The SAP will be developed and finalized for this substudy before any analyses are performed and will describe the analyses and procedures for missing, unused, and spurious data. This section is a summary of the planned statistical analyses of the primary endpoints.

10.8.9.3.1. General Considerations

All safety data will be analyzed separately for each age group (12-17, 18-24, and 25-30 years of age) and for all age groups combined.

Refer to Section 9.3.1 for general considerations of statistical analyses.

10.8.9.3.2. Primary Endpoint(s)/Estimand(s) Analysis

| Endpoint | Statistical Analysis Methods |
|----------|--|
| Safety | Counts and percentages of participants with elevated troponin I levels |
| | before and 4 days and 1 month after administration of BNT162b2 or |
| | placebo will be provided for Sequence 1 and Sequence 2 combined. |
| | The associated Clopper-Pearson 95% CIs will also be provided |
| | (Section 9.3.1.1). |
| | The difference in percentages of participants with elevated troponin I |
| | levels between BNT162b2 and placebo will be provided at each time |
| | point after vaccination (4 days after BNT162b2 minus 4 days after |
| | placebo, or 1 month after BNT162b2 minus 1 month after placebo) |
| | combining Sequence 1 and Sequence 2. This analysis will be limited to |
| | participants with troponin I level measurements at both time points. The |

| Endpoint | Statistical Analysis Methods | | | |
|---|---|--|--|--|
| F | 2-sided 95% CI for the difference in percentages will be calculated using the adjusted Wald interval as described by Agresti and Min (2005) ⁴³ for comparing matched proportions. The difference in percentages of participants with elevated troponin I levels between before and after each vaccination (ie, 4 days after BNT162b2 minus before BNT162b2, 4 days after placebo minus before placebo) and associated 95% CI will be summarized in a similar way. Additional assessment based on the crossover design feature may be performed and details will be described in the SAP. | | | |
| | In addition, percentages of participants with elevated troponin I levels before and at subsequent time points after each vaccination will be summarized for Sequence 1 and Sequence 2 separately. | | | |
| Descriptive statistics will be provided for each reactogenicity end after each vaccination for Sequence 1 and Sequence 2 separately. reactions and systemic events from Day 1 through Day 7 after each vaccination (where Day 1 is the day of vaccination) will be present severity and cumulatively across severity levels. Descriptive sum statistics will include counts and percentages of participants with indicated endpoint and the associated Clopper-Pearson 95% CIs (Section 9.3.1.1). | | | | |
| | Local reactions and systemic events within 7 days after BNT162b2 or placebo administration will also be summarized in a similar way for Sequence 1 and Sequence 2 combined. | | | |
| | AEs and SAEs will be categorized according to MedDRA terms. Counts, percentages, and associated Clopper-Pearson 95% CIs of AEs and SAEs within 1 month after each vaccination will be provided for Sequence 1 and Sequence 2 separately (Section 9.3.1.1). | | | |
| | AEs/SAEs will also be summarized within 1 month after BNT162b2 or placebo administration in a similar way for Sequence 1 and Sequence 2 combined. | | | |

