9.3.1. General Considerations

Each substudy will be reported separately.

CIs for all endpoints in the statistical analysis will be presented as 2-sided at the 95% level unless specified otherwise.

The safety analyses are based on the safety population. Participants will be summarized by vaccine group according to the study interventions they received. Missing reactogenicity e-diary data will not be imputed; missing AE dates will be handled according to the Pfizer safety rules.

For all the immunogenicity endpoints, the analysis will be based on the evaluable immunogenicity population. An additional analysis may be performed based on the all-available immunogenicity populations if there is a large enough difference in sample size between the all-available immunogenicity population and the evaluable immunogenicity population. Participants will be summarized according to the vaccine group to which they were randomized. Missing serology data will not be imputed.

The evaluable efficacy population will be the primary analysis population for all efficacy analyses. Additional analyses based on the all-available efficacy (mITT) population will be performed. Participants will be summarized according to the vaccine group to which they were randomized. Missing laboratory results will not be imputed.

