9.3.1.1. Analyses for Binary Data

Descriptive statistics for categorical variables (eg, proportions) are the percentage (%), the numerator (n) and the denominator (N) used in the percentage calculation, and the 95% CIs where applicable.

The exact 95% CI for binary endpoints for each group will be computed using the F distribution (Clopper-Pearson method). The 95% CI for the between-group difference for binary endpoints will be calculated using the Miettinen and Nurminen method.

The 3-tier approach may be used to summarize AEs for certain substudies (refer to each substudy for specification). For both Tier 1 (if any are identified during the study) and Tier 2 events, a 95% CI for the between-group difference in proportions will be calculated based on the Miettinen and Nurminen method. In addition, for Tier 1 events (if any), the asymptotic p-values will also be presented for the difference in proportions, based on the same test statistic and under the assumption that the test statistic is asymptotically normally distributed. For Tier 3 events, counts and percentages for each vaccine group will be provided.

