10.8.4. Study Design

10.8.4.1. Overall Design

This is a randomized, placebo-controlled, observer-blind, crossover substudy to evaluate the safety and tolerability of a booster (third or fourth) dose of BNT162b2. Participants ≥12 years of age to ≤30 years of age who have received 2 or 3 prior doses of BNT162b2 (30-µg doses), with their last dose at least 4 months (120 days) prior to randomization, will be enrolled. Participants will be randomized at a ratio of 1:1 to receive either BNT162b2 or placebo at Visit 201 and the alternative at Visit 203, four weeks later. Randomization will be stratified by age (stratified as 12-17, 18-24, and 25-30 years of age). Approximately 1500 participants will be randomized in the study. A blood sample will be collected to obtain a serum sample for troponin testing before each administration of blinded study intervention, 2 to 5 days after each administration, and 1 month after the second administration.

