10.8.9.5. Sample Size Determination

The study size is not based on any formal hypothesis test. All statistical analyses will be descriptive.

Table 8 shows the probability of observing at least 1 AE for a given true event rate of a particular AE, for various sample sizes based on anticipated enrollment in each age group and overall. For example, if the true AE rate is 0.10%, with 750 participants in each randomized sequence, there is 53% probability of observing at least 1 AE.

Table 8. Probability of Observing at Least 1 AE by Assumed True Event Rates With Different Samples Sizes

| Sample Size | Assumed True Event Rate of an AE | | | | | | |
|-------------|----------------------------------|-------|-------|-------|-------|-------|-------|
| (N) | 0.01% | 0.02% | 0.05% | 0.10% | 0.50% | 1.00% | 2.00% |
| 250 | 0.02 | 0.05 | 0.12 | 0.22 | 0.71 | 0.92 | >0.99 |
| 500 | 0.05 | 0.10 | 0.22 | 0.39 | 0.92 | >0.99 | >0.99 |
| 750 | 0.07 | 0.14 | 0.31 | 0.53 | 0.98 | >0.99 | >0.99 |
| 1500 | 0.14 | 0.26 | 0.53 | 0.78 | >0.99 | >0.99 | >0.99 |

Note: A total of 250 and 500 participants are to be enrolled in each age group within each randomized sequence and overall. A total of 750 and 1500 participants are to be enrolled for all age groups within each randomized sequence and overall.

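### Substudy B: the adjusted Wald interval for the paired troponin differences gives an upper limit that is too low if discordant pairs prove to be very few

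*Protocol*

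**What the plan says.** Section 10.8.9.3.2 of the protocol compares the percentage of participants with elevated troponin I after BNT162b2 with the percentage after placebo, within participants, at 4 days and at 1 month. It fixes the method: the "2-sided 95% CI for the difference in percentages will be calculated using the adjusted Wald interval" for matched proportions. The before-and-after differences for each injection are handled similarly. Single percentages get Clopper-Pearson limits in the same section.

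The confidence level comes from section 9.3.1: "CIs for all endpoints in the statistical analysis will be presented as 2-sided at the 95% level unless specified otherwise". Section 10.8.4.1 gives the size: "Approximately 1500 participants will be randomized in the study". The analysis is repeated in subgroups. Section 10.8.9.3.1 says "All safety data will be analyzed separately for each age group", and the note to Table 8 says "A total of 250 and 500 participants are to be enrolled in each age group within each randomized sequence and overall". The paired analyses therefore have at most 1500 pairs overall and 500 per age group, less any participant without both measurements.

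Section 10.8.9.1.2 makes all objectives descriptive, with no test. No margin or threshold for the excess is set, and no background rate of elevated troponin I is given.

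**The concern.** The adjusted Wald interval for matched proportions adds 0.5 to each cell of the paired table and then uses a normal standard error. With few discordant pairs the sampling distribution of the difference is strongly skewed, and a symmetric interval puts its upper end too low.

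Substudy B looks for subclinical cardiac injury. If few or no participants show an elevation, readers will look at the upper limit of the excess to see how large a risk is still compatible with the data. A limit at about half its proper value would give more reassurance than the sample supports, most plausibly in the age-group analyses, where counts are smallest.

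**Working it through.** **Inputs.** N = 1500 (section 10.8.4.1) and N = 500 (note to Table 8); two-sided 95%, so z = 1.96 (section 9.3.1). Assumed, because the documents are silent: the rate of placebo-only elevation (0 to 0.5%) and the true excess (0.05% to 0.75%). All pairs are taken as complete. With fewer pairs the limits scale up roughly as 1/N, and the ratios between methods barely change.

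**The plan's own figure.** Section 10.8.9.5 states: "if the true AE rate is 0.10%, with 750 participants in each randomized sequence, there is 53% probability of observing at least 1 AE". Check: 1 - (1 - 0.001)^750 = 0.528. For 1500, 1 - (1 - 0.001)^1500 = 0.777, which is Table 8's 0.78. Zero events in 1500 therefore still has a 22% chance at a true rate of 0.10%.

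**Adjusted Wald.** Let b be the BNT162b2-only and c the placebo-only elevations. The protocol names the method without a formula; its standard form is b* = b + 0.5, c* = c + 0.5, n* = N + 2, d = (b* - c*)/n*, SE = sqrt[(b* + c*) - (b* - c*)²/n*]/n*, limits d ± 1.96 SE.

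- b = c = 0: d = 0 and SE = 1/n*. Upper limit 1.96/1502 = 0.130%; 1.96/502 = 0.390%.
- b = 1, c = 0, N = 1500: d = 1/1502 = 0.0666%, SE = sqrt(2 - 1/1502)/1502 = 0.0941%, upper limit 0.0666 + 1.96 × 0.0941 = 0.251%. The same steps for N = 500 give 0.751%.

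**Comparators.** With c = 0, the exact bound is the Clopper-Pearson upper limit for b/N. For b = 0 it is 1 - 0.025^(1/N). It is valid for the excess, because the excess cannot be larger than the probability of a BNT162b2-only elevation. The score limit is Tango's, by root-finding.

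| N | b (c = 0) | Adjusted Wald | Exact | Score | Exact / adjusted Wald |
|---|---|---|---|---|---|
| 1500 | 0 | 0.130% | 0.246% | 0.255% | 1.88 |
| 1500 | 1 | 0.251% | 0.371% | 0.377% | 1.48 |
| 500 | 0 | 0.390% | 0.735% | 0.762% | 1.88 |
| 500 | 1 | 0.751% | 1.109% | 1.124% | 1.48 |

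At a true excess equal to the zero-event limit of 0.1305%, with no placebo-only elevations, zero events has probability (1 - 0.001305)^1500 = 14.1%. The ratio in the last column falls to 1.19 at 5 events and 1.07 at 20.

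**Upper-side miss rate.** For each background rate and excess, sum the trinomial probabilities of all (b, c) whose upper limit lies below the true excess. Nominal is 2.5%.

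| N = 1500, placebo-only rate | Excess 0.05% | 0.133% | 0.267% | 0.40% |
|---|---|---|---|---|
| 0 | 0.0% | 13.6% | 9.1% | 6.2% |
| 0.05% | 0.2% | 6.5% | 5.3% | 4.7% |
| 0.1% | 0.8% | 3.8% | 4.0% | 4.3% |
| 0.5% | 2.1% | 2.3% | 2.5% | 2.7% |

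Over excesses from 0.13% to 0.75%, the range is 3.5% to 4.7% at a placebo-only rate of 0.1%, and 2.3% to 2.9% at 0.5%. For N = 500 and an excess of 0.40%, the miss rate is 13.5%, 8.2% and 5.2% at placebo-only rates of 0, 0.1% and 0.2%. With no placebo-only elevations it is 0% at excesses of 0.05%, 0.133% and 0.267%.

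**Within one table.** If none of 1500 participants is elevated after either injection, the plan would print an upper limit of 0.246% (Clopper-Pearson) for the BNT162b2 risk and 0.130% for the excess over placebo. With both counts at zero, nothing in the data justifies the tighter figure. The score limit of 0.255% shows that the gap is not merely Clopper-Pearson conservatism.

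**The case against.** The strongest objection is that sparsity is an assumption. Section 10.8.2.1 uses very rare for reported clinical myocarditis and pericarditis, and says that the subclinical frequency is not known. The endpoint here is any elevated troponin I, and placebo-side elevations also count as discordant pairs. Table 8 concerns adverse events in general. A reader might infer that a zero- or one-event table is the expected outcome; the documents do not support that. This objection stands and makes the point conditional.

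Second, the 13.5% figure is a worst case just above the zero-event limit, where a discrete interval drops sharply; below that limit, with no placebo-only elevations, the miss rate is zero. Two-sided coverage is about 95% or better in most N = 1500 scenarios once placebo-only discordance reaches 0.1%. That is true, but the misses remain mostly on the upper side, which matters most for safety.

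Third, the score interval is not uniformly better. It moves error to the lower tail, up to 5.3%. At N = 1500 with 0.05% placebo-only discordance and an excess of 0.267%, its two-sided coverage is 93.1%, against about 94% for adjusted Wald. That stands as a trade-off.

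Fourth, a reader might see a conflict with section 9.3.1.1: "The 95% CI for the between-group difference for binary endpoints will be calculated using the Miettinen and Nurminen method". There is none. That rule concerns independent groups, and section 10.8.9.3.2 correctly names a method for matched data.

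Finally, the counts and exact single-percentage limits would also be shown, so a zero-event result would be visible. This softens the problem but leaves the reported limit for the difference too low.

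**Conclusion.** The point holds as a conditional one. If discordant pairs are very few, the upper limit fixed in section 10.8.9.3.2 is about half the exact limit at zero events and about two thirds of it at one event, overall and within each age group. The upper-side miss rate can then reach about 13.5%. At N = 1500 it is about 4-5% with 0.1% placebo-only discordance, for excesses of 0.13% or more, and near nominal at 0.5%.

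This rests on the standard add-0.5 form of the interval, on complete pairs, and on assumed background rates. A reader might go further and say that the plan claims to rule out an excess risk that its sample cannot exclude. The documents do not support that: they state no margin, decision rule or claim of exclusion. What is at stake is how a near-zero result would be read, so the weight is SHOULD, and minor.

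**What to change.** In section 10.8.9.3.2, or in the SAP, use the paired score (Tango) interval for the troponin differences. Alternatively, keep the adjusted Wald interval and add the score interval when there are about 10 or fewer discordant pairs. In either case give the exact upper bound when the placebo-only count is zero; for the before-and-after differences, the corresponding cell is elevation before injection only. Apply the rule overall and within each age group.

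The cost is about one line of text, with no new data and no change in sample size. In sparse tables the intervals become wider and the upper limits less favourable, and the score method carries somewhat more lower-tail error. With many discordant pairs the results hardly change.

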10.8.9.3.3. Secondary Endpoint(s)/Estimand(s) Analysis

Not applicable.

10.8.9.3.4. Exploratory Endpoint(s)

Not applicable.

10.8.9.4. Interim Analyses

No formal interim analysis will be conducted for this study. Only 1 analysis will be performed at the completion of the study.

10.8.9.4.1. Data Monitoring Committee or Other Independent Oversight Committee

This substudy will use a DMC. The DMC is independent of the study team and includes only external members. The DMC charter describes the role of the DMC in more detail. The DMC will be responsible for ongoing monitoring of the safety data throughout the study according to the charter.

The recommendations made by the DMC will be forwarded to the appropriate Pfizer personnel for final decision. Pfizer will forward such decisions, which may include summaries of aggregate analyses of safety data, to regulatory authorities, investigators as appropriate.

10.8.9.5. Sample Size Determination

The study size is not based on any formal hypothesis test. All statistical analyses will be descriptive.

Table 8 shows the probability of observing at least 1 AE for a given true event rate of a particular AE, for various sample sizes based on anticipated enrollment in each age group and overall. For example, if the true AE rate is 0.10%, with 750 participants in each randomized sequence, there is 53% probability of observing at least 1 AE.

Table 8. Probability of Observing at Least 1 AE by Assumed True Event Rates With Different Samples Sizes

| Sample Size | Assumed True Event Rate of an AE | | | | | | |
|-------------|----------------------------------|-------|-------|-------|-------|-------|-------|
| (N) | 0.01% | 0.02% | 0.05% | 0.10% | 0.50% | 1.00% | 2.00% |
| 250 | 0.02 | 0.05 | 0.12 | 0.22 | 0.71 | 0.92 | >0.99 |
| 500 | 0.05 | 0.10 | 0.22 | 0.39 | 0.92 | >0.99 | >0.99 |
| 750 | 0.07 | 0.14 | 0.31 | 0.53 | 0.98 | >0.99 | >0.99 |
| 1500 | 0.14 | 0.26 | 0.53 | 0.78 | >0.99 | >0.99 | >0.99 |

Note: A total of 250 and 500 participants are to be enrolled in each age group within each randomized sequence and overall. A total of 750 and 1500 participants are to be enrolled for all age groups within each randomized sequence and overall.

10.9. Appendix 9: Substudy C

10.9.1. Substudy Summary

10.9.1.1. Synopsis

See Section 1.1 for a synopsis of Substudy C.

10.9.1.2. Schema

| | Visit Number | 301 | 302 | 303 | 304 |
|---------------------|-------------------|---------------------|--------------|---------------|----------------|
| | Visit Description | Booster (Third) | 7 Days After | 1 Month | 6 Months After |
| | | Dose of BNT162b2 | Booster | After Booster | Booster |
| | | | Vaccination | Vaccination | Vaccination |
| Participants having | | BNT162 | | | |
| received 2 prior | | 10-μg OR 30-μg dose | | | |
| doses of 30 µg | | | | | |
| BNT162b2 at least | | | | | |
| 5 months (150 days) | | | | | |
| prior to | | | | | |
| randomization | | | | | |
| | Blood draw for | X | X | X | X |
| | immunogenicity | | | | |

10.9.1.3. Schedule of Activities for Substudy C

| Visit Number | 301 | 302 | 303 | 304 |
|---|-------------------------------------|-------------------------------------|--------------------------------------|---------------------------------------|
| Visit Description | Booster (Third) Dose of BNT162b2 | 7 Days After Booster Vaccination | 1 Month After Booster Vaccination | 6 Months After Booster Vaccination |
| Visit Window | Day 1 ^a | 6-8 Days After Visit 301 | 28 to 35 Days After Visit 301 | 175-189 Days After Visit 301 |
| Confirm the participant has only received 2 doses of BNT162 at least 5 months (150 days) prior to randomization. | X | | | |
| Obtain informed consent/assent | X | | | |
| Obtain the participant's prior study and participant number (if applicable) | X | | | |
| Assign participant number | X | | | |
| Obtain demography and medical history data | X | | | |
| Perform clinical assessment ^b | X | | | |
| For participants who are HIV-positive, record latest CD4 count and HIV viral load | X | | X | X |
| Measure height and weight | X | | | |
| Measure temperature (body) | X | | | |
| Perform urine pregnancy test (if appropriate) | X | | | |
| Confirm use of contraceptives (if appropriate) | X | X | X | |
| Collect nonstudy vaccine information | X | X | X | |
| Collect prohibited medication use | | X | X | X |
| Confirm eligibility | X | | | |
| Review temporary delay criteria | X | | | |
| Collect blood sample for immunogenicity ^c | ~10 mL | ~10 mL | ~10 mL | ~10 mL |
| Obtain randomization number | X | | | |
| Obtain study intervention allocation | X | | | |
| Administer study intervention | X | | | |
| Assess acute reactions for at least 30 minutes after study intervention administration | X | | | |
| Explain/review participant communication methods (including for reactogenicity e-diary completion), assist the participant with downloading the app, or issue provisioned device, if required | X | | | |
| Provide/ensure participant has a thermometer and measuring device | X | | | |

| Visit Number | 301 | 302 | 303 | 304 |
|---|-------------------------------------|-------------------------------------|--------------------------------------|---------------------------------------|
| Visit Description | Booster (Third) Dose of BNT162b2 | 7 Days After Booster Vaccination | 1 Month After Booster Vaccination | 6 Months After Booster Vaccination |
| Visit Window | Day 1 ^a | 6-8 Days After Visit 301 | 28 to 35 Days After Visit 301 | 175-189 Days After Visit 301 |
| Review reactogenicity e-diary data (daily review is optimal during the active diary period of 7 days following study intervention administration) | $X \rightarrow$ | $X \rightarrow$ | | |
| Review ongoing reactogenicity e-diary symptoms with participant and obtain stop dates | | X | X | |
| Request the participant return the e-diary or assist the participant to delete the application | | | X | |
| Collect AEs and SAEs as appropriate | X | X | X | X ^d |

Abbreviation: HIV = human immunodeficiency virus.

- a. The visit may be conducted across 2 consecutive days; if so, all steps from assessing the inclusion and exclusion criteria onwards must be conducted on the same day.
- b. Including, if indicated, a physical examination.
- c. 10 mL is to be collected from participants 12 to 17 years of age.
- d. Any AEs occurring up to 48 hours after the blood draw must be recorded (see Section 8.3.1).

